3.7.3 Exploratory Pharmacokinetic Endpoints

A population PK analysis approach will be implemented to assess the pharmacokinetics of intravenous phenobarbital in neonatal seizures. The following phenobarbital pharmacokinetic parameters may be *explored* during the study:

- Observed time to reach maximum drug concentration (Tmax)
- Observed peak drug concentration (Cmax)
- Area under the plasma concentration-time curve (AUC_{0-t}), the percent AUC extrapolated from AUC_{0-t} to infinity AUC_{extrap} and infinity (AUC_{0-inf})
- Apparent terminal elimination rate constant (K_{el})
- Apparent terminal drug elimination half-life (t_{1/2})
- Clearance adjusted by absorption, calculated as dose/AUC_{0-inf} (Cl/F)
- Volume of distribution adjusted by absorption, calculated as Dose/K_{el}•AUC_{0-inf} (V_d/F)

CONFIDENTIAL

4. ANALYSIS POPULATIONS

The membership of each analysis set will be determined and documented by the Medical Monitor, data manager and the trial statistician, the reasons for exclusion will be given prior to database lock. A summary table will list the individual subjects sorted by treatment group and describe their protocol deviation/violation.

The analysis populations will be listed as follows:

4.1. Intention-to-treat (ITT) population:

Intention-to-treat (ITT) population: Subject population consists of all randomized subjects with valid informed consent.

Analyses for efficacy, tabulations of demographic and baseline characteristics, population disposition and important protocol deviation will utilize this analysis set.

4.2. Per-protocol (PP) population:

A subset of the ITT population. Subjects with major protocol deviations will be excluded from ITT population if they have any of the following major protocol deviations:

- Subjects who did not qualify for randomization but were inadvertently randomised into the study
- Randomized but was given treatment wrongly

This population will be used for the supportive analyses.

4.3. Safety population:

Subject population consist of all randomized subjects who receive at least one dose or partial dose of study drug.

Subjects will be analysed according to the randomised treatment unless a subject has received the incorrect treatment during the entire study period. Analysis for safety endpoints will utilize this analysis set.

4.4. Pharmacokinetic (PK) population:

Study participants that received at least 1 dose from the same study arm (as per randomization or per error) are included in this population group.

CONFIDENTIAL**5. GENERAL CONSIDERATIONS FOR DATA ANALYSES****5.1. Reporting guidelines**

We will follow the Consolidated Standards of Reporting Trials (CONSORT) 2010 statement: updated guidelines for reporting parallel group randomised trials (<http://www.consort-statement.org/>).

5.2. Data Summaries

Continuous variables will be summarised according to number of subjects with non-missing data (n), mean, standard deviation (SD), median, minimum, and maximum.

Categorical variables will be summarised according to the absolute frequency and percentage of subjects (%) in each category level. The denominator for the percentages is the number of subjects in the treatment arm with data available, unless noted otherwise.

5.3. Planned Covariates

Covariate analyses will be performed on the primary outcome on the ITT population. The prespecified covariates in this study will be:

Stratification factors

- Presence or absence of HIE
- High or low seizure burden

Baseline values

- Gender (binary)
- Gestational age (continuous)
- birth weight (continuous)
- Apgar scores (continuous)
- Liver function tests (Total Protein, Albumin, Bilirubin, ALP, AST, ALT) (continuous)
- Seizure etiology (binary)
- pre-treatment seizure burden (continuous)

5.4. Subgroup

Subgroup analysis for primary outcome on the ITT population will be performed in a series of predefined strata, which was defined as below. Imputation for these baseline missing covariates will be carried out before categorizing.

Grouping Variable	Subgroups
Gender	Male or Female

CONFIDENTIAL

Birth weight	Dichotomised at median
Apgar scores	Dichotomised at median
Liver function tests (Total Protein, Albumin, Bilirubin, ALP, AST, ALT)	Dichotomised at median
Seizure etiology	Yes or No
Therapeutic hypothermia	Yes or No
Pre-treatment seizure burden	Dichotomised at median

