4.1 Overall Design

This is a multicenter, randomized, double-blinded, active-controlled, parallel study in neonates (defined as ≥ 34 - ≤ 44 gestational weeks). The study will consist of a Screening Period, Double-Blind Treatment Period, Follow-up Period and an Open-Label Extension Period. The study participant population is neonates being admitted to the NICU and requiring continuous video electroencephalography (cvEEG) for seizure detection. One or two parents and/or legal guardians must provide written approval of informed consent, before the neonate can be assessed, monitored and managed in accordance with the study protocol and before any study data can be collected and recorded as study data. The reviewing IRB, based on its standard operating procedures, will determine number of parents/legal guardians who will be required to sign the informed consent.

Upon NICU admission and after parents or legal guardians provide informed consent, neonates will be monitored for electrographic seizures.

Seizures requiring study drug treatment will be defined as cumulative electrographic seizure of at least 30 sec/h (22). Confirmation of electrographic seizures by principal investigator or site designees (recommended to be a pediatric neurologist and/or neurophysiologist) is required. Randomization and study drug administration should start as soon as possible after the 30 sec/h of seizure activity criteria is met ideally within 30 min (maximum two hours) (22). If study drug cannot be administered within two hours of recognition of qualifying seizure burden (≥ 30 sec/h), then study drug should not be administered and the neonate will be discontinued from the study and will be a screen failure.

Following confirmation of seizure criteria, neonates will be randomized in a 1:1 allocation to receive a phenobarbital treatment loading dose of 20mg/kg or 40mg/kg, infused over 30 minutes.

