9.1 Statistical Hypothesis

This study was designed to show that high dose phenobarbital (40 mg/kg) is more effective than low dose phenobarbital (20 mg/kg) following single dose administration in terms of study's primary endpoint ([Section 3.2.1](#)). Specifically, the following primary statistical hypotheses will be tested.

Null hypothesis H_0 : there is no difference between treatments in the proportion of participants having a primary efficacy endpoint.

Alternative hypothesis H_a : The proportions of participants having a primary efficacy endpoint are different between the two treatment groups.

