3.6. Sample Size

Literature supports that lower loading doses of phenobarbital achieve seizure control in approximately 30 to 60% of treated neonates, with higher loading doses achieving seizure control up to 85%. Based on an effect size of 20% (from 50% in the low dose group to 70% in the high dose group), an alpha of 0.05 and 80% power, it is estimated that the number of completed subjects required will be 93 subjects in each group (total 186). With approximately, 5% dropout resulting in non-evaluable primary outcome, the minimum required for randomization will be 196.

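### Nine of the twelve subgroup interaction tests use only a median cut of a continuous variable; adding a continuous interaction test would recover information if the dose effect changes gradually

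*SAP*

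**What the plan says.** SAP 5.4 lists the subgroup variables. Sex, seizure etiology and therapeutic hypothermia are two-level. For birth weight, Apgar scores, the six named liver tests (total protein, albumin, bilirubin, ALP, AST, ALT) and pre-treatment seizure burden the entry is "Dichotomised at median".

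SAP 7.1.4 tests homogeneity of the dose effect with a binomial, log-link GLM containing treatment, the subgroup variable and their interaction, and reports the interaction P-value. No interaction test with the covariate left uncut appears anywhere in the SAP.

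SAP 5.3 lists the same variables for the adjusted analysis uncut, for example "birth weight (continuous)" and "pre-treatment seizure burden (continuous)". Apgar and the liver tests carry the same label.

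Protocol 9.4.7 asks for predefined strata but specifies no median cut, so the cut is an SAP choice. SAP 5.6 calls additional analyses of the primary outcome exploratory. SAP 7.1.4 makes no multiplicity adjustment for subgroups and warns of false positives.

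**The concern.** A median cut treats a neonate just above the median like the most extreme one. If the benefit of the higher dose rises or falls gradually with a covariate, the cut throws away part of the evidence for that. The cutpoint also depends on the sample, and on a 0 to 10 integer scale such as Apgar, ties can prevent an even split.

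The primary objective is dose-response, so whether the dose effect varies with, say, baseline seizure burden is a natural follow-up question. Interaction tests are weak at this sample size in any case. A non-significant result from a further weakened test could be read as evidence of homogeneity, and the SAP's caution covers false positives only.

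**Working it through.** **1. The plan's own sample size.** SAP 3.6 assumes a change "from 50% in the low dose group to 70% in the high dose group", with "an alpha of 0.05 and 80% power". The test is two-sided, because Protocol 9.1 states the alternative as "The proportions of participants having a primary efficacy endpoint are different between the two treatment groups". Protocol 4.1 says "neonates will be randomized in a 1:1 allocation". With pooled variance:

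n per group = [1.96·√(2·0.6·0.4) + 0.842·√(0.7·0.3 + 0.5·0.5)]² / 0.2² = (1.358 + 0.571)² / 0.04 = 93.

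SAP 3.6 allows for "5% dropout resulting in non-evaluable primary outcome": 186/0.95 = 195.8, so 196. Both stated figures reproduce. The documents give no power figure for any interaction test.

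**2. The count.** Cut at the median: birth weight 1 + Apgar 1 + liver tests 6 + seizure burden 1 = 9. Not cut: sex, etiology, hypothermia = 3. Total 12. This takes Apgar and bilirubin as one variable each. The protocol records Apgar at 1, 5 and 10 minutes and bilirubin as total and direct; if each were tested, the count would be 12 of 15. Protocol 9.4.7 also names gestational age and pre-consent seizure burden, which are not in the SAP table.

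**3. Information kept by the cut.** Under 1:1 randomisation and a linear interaction, the efficiency of the split relative to the continuous test is the squared correlation between X and the indicator X > median, that is cov² / (var X · ¼). The documents give no covariate distributions, so the shapes are assumptions.

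| Assumed shape of X | Efficiency | Loss |
|---|---|---|
| Uniform | (1/8)² / (1/12 · 1/4) = 0.75 | 25% |
| Normal | (1/2π) / (1/4) = 2/π = 0.637 | 36% |
| Exponential, raw scale | (ln 2)² = 0.480 | 52% |
| Lognormal, log-SD 0.5, raw scale | 0.1915² / (0.25 · 0.2840) = 0.516 | 48% |
| Lognormal, log-SD 1, raw scale | 0.3413² / (0.25 · 1.718) = 0.271 | 73% |

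Assumed Apgar-like integer scores give losses of 30% to 38%. A lognormal covariate whose interaction is linear on the log scale returns to 36%. In the normal case, 196 neonates carry the interaction information of 196 × 0.637 ≈ 125.

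**4. Power at N = 196, risk-difference (RD) scale, normal covariate, linear interaction.** The SE of the main RD is √(0.21/98 + 0.25/98) = 0.0685. This is also approximately the SE of the RD slope per SD. Between two equal halves the SE of the interaction is 2 × 0.0685 = 0.137. A slope b per SD separates the halves by 2 × 0.798 × b.

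- b = 0.10: continuous z = 0.10/0.0685 = 1.46, power 31%. Split z = 0.160/0.137 = 1.16, power 21%.
- b = 0.15: continuous z = 2.19, power 59%. Split z = 0.239/0.137 = 1.75, power 42%.

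Simulations with a linear probability model and robust SE gave 32–33% against 21–23% for b = 0.10, and 61–63% against 41–42% for b = 0.15. False-positive rates were about 5% to 6% for both tests.

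**5. The opposite case.** Suppose the RD is 5 points below the median and 35 above it. The split then tests a 30-point difference: z = 0.30/0.137 = 2.19, power about 59%. The linear test has z ≈ 2.19 × 0.798 = 1.75, power about 42%. Simulation gave 55–57% for the split and 42–43% for the continuous test.

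**6. Log transform and imputation.** SAP 5.5.1 draws missing continuous values from a normal distribution with the sample mean and SD, and SAP 5.4 imputes before cutting. For a lognormal variable the share of negative draws is Φ(−1/CV), with CV = √(exp(σ²) − 1). At log-SD 0.5, CV = 0.533 and the share is 3%. At log-SD 1, CV = 1.311 and it is 22%. A median cut tolerates such values; a log does not.

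**The case against.** The strongest reply is that nothing decisive rests on these tests. They are exploratory, the SAP tells the reader to be cautious, the primary analysis is untouched, and both approaches have similar false-positive rates. A prespecified median cut is common and easy to read. All of this stands, and it limits the point to a cheap improvement.

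A reader might infer that the cut costs about a third of the information in all nine tests. The documents do not support that: they give neither covariate distributions nor a reason to expect linearity, and the loss ranges from nil to 73% over plausible shapes. A reader might also infer that the continuous test should replace the split. It should not, because for a step at the median the split has more power (step 5 of the working). The two tests are complementary.

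Three further objections hold in part. The power figures are on the RD scale under a linear model, whereas SAP 7.1.4 uses a log link; no power has been calculated for the planned test. A slope of 10 or 15 points per SD around a 20-point RD is a large interaction, and at 10 points both tests are weak. Finally, pre-treatment seizure burden may not be captured in full. Protocol 8.1.1.1 asks for the start and end of each seizure, but the recording guidelines in 8.1.4 begin at the first dose. Entry also requires at least 30 seconds per hour, so burden has a floor and is probably skewed.

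**Conclusion.** The point holds as a minor, inexpensive improvement. On the SAP's own list, nine of twelve interaction tests rely solely on a median cut of a variable that the SAP elsewhere keeps continuous.

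The cost is conditional. It is about 36% of the interaction information if the covariate is roughly normal on the analysed scale and the dose effect changes linearly with it, and it varies with shape as tabulated. At 196 neonates this means roughly 10 points of power lost for a 10-point slope per SD and 20 points lost for a 15-point slope, on the RD scale. These figures rest on assumed distributions, not on anything in the documents.

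It does not follow that the planned tests are invalid, that their error rate is inflated, or that the primary conclusion is at risk.

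**What to change.** In SAP 5.4 and 7.1.4, keep the planned median-split subgroup estimates and interaction tests. For each of the nine variables, add a prespecified test of treatment by continuous covariate (per SD), with the same outcome coding and the same log link and risk ratio as the planned test. Moving to the RD scale would change the null hypothesis and is not needed for this purpose. Name a fallback in case the log-binomial model does not converge, such as modified Poisson regression with a robust SE.

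State in advance which liver tests, and whether seizure burden, will be log-transformed. For those, impute missing values on the log scale or use complete cases. State also which Apgar time and which bilirubin fraction are meant.

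The cost is some SAP text, nine short models and a small change to imputation for transformed variables; no new data are needed. The downsides are nine more exploratory P-values, and a linear-trend assumption that has less power than the split if the true pattern is a step at the median.

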5.5. Missing data**5.5.1. Baseline covariates**

Missing baseline covariates will be imputed using simple imputation methods in the covariate adjusted analysis based on the covariate distributions. For a continuous variable, missing values will be imputed from random values from a normal distribution with mean and SD calculated from the available sample. For a categorical variable, missing values will be imputed from random values from a uniform distribution with probabilities $P1, P2, \dots, Pk$ from the sample. For a count data, missing values will be imputed from random values from a Poisson distribution with λ from the sample. Seed for the imputation is set as 128.

5.5.2. Primary outcome

Randomised subjects with missing responses will be treated as treatment failures

5.5.3. Other Outcomes (e.g. Safety, secondary outcomes etc.)

No imputation will be performed

5.6. Multiplicity

Analysis for secondary outcome and additional analysis for primary outcome are regarded as exploratory in nature, therefore, multiplicity adjustment will not apply to the primary and secondary outcome analyses.

CONFIDENTIAL**5.7. Interim Analyses**

Due to the small sample size of the study population, an interim analysis will not be performed.

5.8. Software

SAS® (version 9.4) will be used to perform all data analyses and generate the data displays or listing.

6. SUBJECT DISPOSITION, BACKGROUND AND DEMOGRAPHIC CHARACTERISTICS**6.1. Participant disposition and Flow chart**

A flow chart will be drawn up showing the number of subjects screened, enrolled, randomised, and followed-up in each study arm, and the number contributing to the ITT, PP and safety analysis.

The number screened and not enrolled and the reasons for non-enrolment will be reported by randomized treatment group and for all randomized subjects combined, along with the number of subjects who were lost to follow up (with reasons), and the number who withdrew for safety reasons, and who crossed over between study arms (if happened).

6.2. Demographics and Other Baseline Characteristics

Demographic and baseline characteristics will be summarized by randomized treatment group and for all randomized subjects combined on ITT population. Data will be presented following the reporting convention above for continuous and/or categorical variables.

Any imbalances between treatment groups for the characteristics will be assessed when reviewing the summary tabulations and any differences deemed clinically relevant to the safety or efficacy comparisons may be investigated by controlling for the characteristic in an exploratory way.

6.3. Medical history

Any condition entered on the relevant medical history / current medical conditions CRF will be coded using the MedDRA dictionary. Medical history is collected at Screening visit. The number and percentage of subjects with each medical condition will be provided by treatment group and overall, and system of organ class for the ITT population.

6.4. Treatment exposure

Average dose and dose level will be summarized by visit and overall study and treatment group (mean, standard deviation, median, minimum and maximum). Average dose will be calculated on the safety population.

CONFIDENTIAL**6.5. Prior and Concomitant medication**

The concomitant medication information will be summarized based on the safety population.

Prior and concomitant medications will be assigned a 12-digit code using most recent version of the World Health Organization drug codes. Prior and concomitant medications will be further coded to the appropriate Anatomical-Therapeutic-Chemical (ATC) code indicating therapeutic classification. The number (%) of subjects who use a drug will be summarized overall and by treatment by all 4 ATC class.

Prior and concomitant medications by drug and drug class will be listed.

7. STATISTICAL HYPOTHESIS, MODEL, AND METHOD OF ANALYSIS

The principle of ITT will be the main strategy of the analysis adopted for the primary outcome and the secondary outcomes. Analysis among PP population will be deemed as supportive evidence. The safety analysis set will be used to analyse safety endpoints.

7.1. Primary Outcome Analysis**7.1.1. Primary analysis**

The primary outcome in this trial is whether a neonate requires additional seizure treatment after the first dose of phenobarbital during the first 24 hours after treatment, which will be summarized by percent of neonates who do not require additional seizure treatment after the first dose of phenobarbital during the first 24 hours after treatment. The primary analysis will be based on the ITT as defined above.

The primary endpoint will be summarized by number and percent of participants with events by treatment and overall.

The primary hypothesis to be tested is $H_0: \pi_1 - \pi_2 = 0$ versus $H_1: \pi_1 - \pi_2 \neq 0$, where π_1 and π_2 are rates of primary outcome for high dose and low dose group, respectively. The primary efficacy variable will be analyzed using generalized linear model (GLM) with treatment as a study variable, HIE (presence or absence) and seizure burden (high or low) as covariates. Rate difference (RD) together with its 95% confidence interval (CI) will be derived with binomial distribution and identify link function in the GLM model. The estimated risk ratio/relative risk (RR) and its 95% CI will also be provided with binomial distribution and log link function instead.

The above identity-binomial GLM model may not converge when all covariates are introduced into the model simultaneously. To avoid non-convergence issue, we will first calculate a propensity score with treatment as the dependent variable (1 for treatment A and 0 for treatment B) and all covariates listed above as independent variables through a logistic regression model, and then include the calculated propensity score (continuous variable) as a covariate in the identity-binomial GLM model.

CONFIDENTIAL

7.1.2. Per-protocol analysis of the primary outcome

A supportive analysis of the primary outcome will also be performed using the same primary analysis model for per-protocol populations.

7.1.3. Covariate adjusted analysis of the primary outcome

Adjusted analyses will be carried out on the analysis of the primary endpoint to determine whether the treatment effect estimate, or standard error is affected with the inclusion of additional covariates. The prespecified covariates that will be included in the adjusted analyses are described in the sections **5.3 planned covariates**.

The GLM model may not converge when all covariates are introduced into the model simultaneously. To avoid non-convergence issue, we will first calculate a propensity score with treatment as the dependent variable (1 for high dose group and 0 for low dose group) and all covariates listed above as independent variables through a logistic regression model, and then include the calculated propensity score (continuous variable) as a covariate in the GLM model.

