6.3 Measures to Minimize Bias: Randomization and Blinding

Study participants will be assigned unique study participant numbers upon completion of the Screening Period and upon achieving the seizure criteria.

A unique randomization number will be assigned by an interactive web response system (IWRS) once eligibility for the Treatment Period of the study has been determined. Randomization codes will be prepared by an external-to-study, unblinded biostatistician.

Detailed instructions for contacting the IWRS will be provided in the Study Manual. The PI or designee will use the IWRS to determine which investigational medicinal product (IMP) will be

dispensed to a given study participant for the Treatment Period of the study. The unblinded investigational pharmacist will prepare the IMP (both first and second loading dose for each treatment arm [labeled A and B in IWRS for unblinded pharmacist]) after the informed consent is signed and provide to the PI or designee for storage in the NICU's pyxis machine, if possible. At time of randomization, the PI or designee will contact the IWRS for the randomization code and syringe code prior to first dose administration. The IWRS will be contacted again if second loading dose administration is needed.

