9.4.2 Analysis of the Primary Efficacy Endpoint(s)

The primary endpoint will be summarized by number and percent of participants with events and compared by a log binomial model (a generalized linear model [GLM]) that includes treatment as a study variable, which will generate risk ratio (RR) together with their 95% CIs of having a primary outcome between high dose and low dose groups. A study participant who is withdrawn from the study within the first 24 hours after treatment will be considered not to have achieved the primary endpoint. Treatment of such dropouts with respect to other endpoints will be specified in the SAP.

In addition, covariate adjustment will be performed by GLM model with treatment as a study variable and, gender, gestational age, birth weight, apgar scores, liver function tests, seizure etiology, therapeutic hypothermia and pre-treatment seizure burden as covariates. From this

model, adjusted RR together with their 95% confidence interval will be derived. Imputation for these baseline missing covariates will be carried out for adjusted analysis.

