3.4. Randomisation

Subjects will be assigned unique subject numbers upon completion of the Screening Period and upon achieving the seizure criteria.

CONFIDENTIAL

A unique randomization number will be assigned by an interactive web response system (IWRS) once eligibility for the Treatment Period of the study has been determined. A permuted block randomization list will be prepared by an external-to-study, unblinded biostatistician.

Detailed instructions for contacting the IWRS will be provided in the Study Manual. The PI or designee will use the IWRS to determine which IMP will be dispensed to a given subject for the Treatment Period of the study. The unblinded investigational pharmacist will prepare the IMP and provide to the PI or designee for administration.

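### SAP 7.1.3 names no variance that allows for estimating its propensity score, so the default SE cannot show the precision gain the analysis is meant to look for

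*SAP*

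**What the plan says.** SAP 7.1.3 gives its purpose as "to determine whether the treatment effect estimate, or standard error is affected with the inclusion of additional covariates". It does not enter the SAP 5.3 covariates. It regresses treatment on them in a logistic model, "and then include the calculated propensity score (continuous variable) as a covariate in the GLM model". The reason given is possible non-convergence. The section states no link, and neither the SAP nor Protocol 9.4.2 names a robust, stacked or bootstrap variance for this step.

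The model to which covariates are being added is SAP 7.1.1, which already has "HIE (presence or absence) and seizure burden (high or low) as covariates".

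Protocol 9.4.2 describes the adjusted analysis differently: "covariate adjustment will be performed by GLM model with treatment as a study variable and, gender, gestational age" and the rest of its list enter directly, an adjusted RR is reported, and there is no propensity score. That list includes therapeutic hypothermia. SAP 5.3 does not, although SAP 5.4 keeps it as a subgroup.

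Three related provisions matter:

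- For continuous covariates, SAP 5.5.1 says "missing values will be imputed from random values from a normal distribution with mean and SD calculated from the available sample".
- SAP 5.3 lists HIE and seizure burden under "Stratification factors". SAP 3.4 says only "A permuted block randomization list will be prepared by an external-to-study, unblinded biostatistician", and Protocol 6.3 only "Randomization codes will be prepared by an external-to-study, unblinded biostatistician". Neither mentions strata.
- SAP 5.6 classes additional analyses of the primary outcome as exploratory.

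**The concern.** A score that predicts a randomised treatment carries nothing but chance imbalance. Adjusting for it removes that imbalance from the estimate, so the estimate really does become more precise when the covariates are prognostic. But the score explains almost none of the outcome variance, so the fitted model does not register the gain. A model SE that takes the score as known is therefore nearly constant. It cannot answer the SE half of the question that 7.1.3 asks.

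At stake are the confidence interval and the precision statement of a supportive analysis. If the covariates matter, the report would show a slightly larger SE where precision had improved, with intervals that are too wide and some lost power.

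**Working it through.** **1. Design figures.** SAP 3.6 gives 70% vs 50%, alpha 0.05 and 80% power. With a two-sided pooled test, n per arm = [1.960·√(2·0.6·0.4) + 0.842·√(0.21 + 0.25)]² / 0.20² = 93, and 186/0.95 gives 196. Both match the plan. With 98 per arm the unadjusted SE of the risk difference (RD) is √[(0.21 + 0.25)/98] = 0.0685; the simulated mean is 0.068.

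**2. Number of terms.** SAP 5.3 gives HIE, high/low burden, gender, gestational age, birth weight, Apgar, six liver tests, etiology and pre-treatment burden: 14. Protocol 8.2.4 scores Apgar at three times (+2) and Protocol 12.4 lists total and direct bilirubin (+1), so the count runs from 14 to 17.

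**3. Formula check.** With p terms unrelated to treatment, the expected R² of treatment on the covariates is p/(n−1). If the residual outcome variance does not fall, the SE rises by 1/√(1 − p/(n−1)). For n = 196 this is 1.038 at p = 14, 1.044 at 16 and 1.047 at 17. A linear-probability check at moderate strength (covariate predictor SD 1.0 on the logit scale) shows the mechanism. Relative to unadjusted, the SE is 0.952 with the covariates entered directly and 1.033 with the score. The true SD of the score-adjusted estimate is 0.946 of the unadjusted one.

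**4. Main simulation.** 196 infants, 70% vs 50% (60% in both arms for the null), 14 terms, identity link, SAP 5.5.1 imputation, 5,600 trials per scenario. Assumed odds ratios for HIE / log burden per SD / three others per SD: none 1/1/1, weak 1.5/1.5/1.2, moderate 2/2/1.5, strong 3/3/2. Also assumed: HIE in 60%, blocks of 4, liver panel missing in 10%, Apgar in 5%. Each pair is unstratified / stratified allocation, because the documents do not settle which applies.

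| Strength | True SD, unadjusted | True SD, score | Score SE | SE ÷ SD | Null rejection, % |
|---|---|---|---|---|---|
| None | 0.0688 / 0.0683 | 0.0716 / 0.0708 | 0.0705 / 0.0701 | 0.98 / 0.99 | 5.4 / 5.3 |
| Weak | 0.0684 / 0.0672 | 0.0693 / 0.0687 | 0.0703 / 0.0700 | 1.015 / 1.02 | 4.4 / 4.6 |
| Moderate | 0.0684 / 0.0674 | 0.0651 / 0.0654 | 0.0701 / 0.0699 | 1.08 / 1.07 | 3.3 / 4.0 |
| Strong | 0.0682 / 0.0641 | 0.0590 / 0.0588 | 0.0699 / 0.0697 | 1.185 / 1.185 | 2.1 / 2.1 |

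The score SE stays between 0.0697 and 0.0705, that is 2-4% above 0.068, while the true SD moves from 0.0716 to 0.0588.

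**5. Against SAP 7.1.1.** From none to strong, the true SD changes by +3/+3, +2/+2, −2/−3 and −9/−8%. The reported SE changes by +3/+3, +4/+4, +5/+5 and +6/+6%. At moderate or strong strength the score SE exceeds the 7.1.1 SE in 94-95% of trials.

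**6. Sensitivity to strength and scale.** A second set-up (3,000 trials per setting) expressed strength as the SD of the logit predictor. The SE overstated the true SD by about 4-10% at SD 1.0, 13-14% at 1.5 and 20-21% at 2.0. Stratified linear-probability checks were somewhat higher at the top end (1.18 at SD 1.5 and 1.24 at 2.0). On log RR the rise over the unadjusted SE was smaller, about 1-2.5%. With the log link in the main set-up, SE ÷ SD was 1.06-1.08 (moderate) and 1.15-1.17 (strong).

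**7. Which change repairs it.** At logit SD 1.0 the true SD of the score estimate was 0.0643. The model SE was 0.0701, a sandwich SE treating the score as known was also 0.0701, and a bootstrap refitting the score gave 0.0653. Bootstrap SEs for the refitted score and for logistic standardisation, under the main odds ratios (unstratified, no imputation), were:

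| Strength | Refitted score | Standardisation |
|---|---|---|
| None | 0.0714 | 0.0714 |
| Weak | 0.0691 | 0.0691 |
| Moderate | 0.0653 | 0.0651 |
| Strong | 0.0602 | 0.0593 |

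Power with the bootstrap was 86.0% for both at moderate strength, and 90.6% vs 92.0% at strong (Monte Carlo error about 1.3 points). With the model SE, the score had 82.1/82.2% and 84.9/83.9% in the main simulation. Standardisation with a bootstrap SE had SE ÷ SD 0.98-1.03 and null rejection 4.7-5.1% in every scenario.

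**8. Convergence.** With all 14 covariates entered directly, the identity model converged in at most 9% of trials and the log model in under 1%. The score model failed in up to 7.5% (identity) and about 16% (log). At least 99.96% of resampled logistic fits converged. Failed fits were excluded, and failure rates in SAS may differ.

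**The case against.** The strongest reply is that the score is a legitimate estimator and only its SE is off. That stands. With the same bootstrap, the score and standardisation agree closely, so nothing here requires the sponsor to abandon the score. A reader might infer from the higher power of standardisation with a bootstrap that the score itself loses power; step 7 shows that nearly all of that difference is bootstrap against model SE.

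A second reply is that the stakes are small. A rise of about 0.002 on 0.068 may simply be read as an SE hardly affected, the analysis is exploratory under SAP 5.6, and prognostic strength is assumed. All of this stands and limits the weight of the point. It does not make the reported SE right when the covariates are prognostic.

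A third reply concerns the comparator and scale. The SAP plans no unadjusted model; Protocol 9.4.2's treatment-only comparison is not carried into it. Protocol 9.4.2 reports the adjusted result as an RR, where the rise is smaller. Both stand. The comparison should be with 7.1.1, and the 2-4% figure belongs to the RD scale only.

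A reader might also infer that false positives increase or that the primary result is compromised. The figures do not support this. Null rejection is about nominal (5.3-5.4%) with uninformative covariates and below nominal otherwise. The two-covariate score in SAP 7.1.1 has an SE about right (SE ÷ SD 0.99-1.03).

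**Conclusion.** The point holds in a limited form. As written, SAP 7.1.3 yields an SE that does not respond to how much the covariates explain, so it cannot show the gain it is meant to detect. On the RD scale the SE overstates the true SD by roughly 4-10% with moderate covariates and 13-21% with strong ones, and is about right with weak or uninformative ones. The real gain missed relative to 7.1.1 is modest: about 2-3% of the SD at moderate strength and 8-9% at strong, with Monte Carlo error near 1% on each SD.

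These sizes rest on assumed prognostic strengths, covariate correlations and missingness, on 14 terms, and on the default model SE being the one reported. At 17 terms the picture is the same (score SE 4% above unadjusted; SE ÷ SD 1.00, 1.04, 1.08 and 1.17 from none to strong). The error is conservative and confined to a supportive analysis. It is worth correcting because the correction is cheap and specific.

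**What to change.** In SAP 7.1.3, name the variance: a bootstrap stratified by arm that repeats the SAP 5.5.1 imputation and refits every step in each resample, including the score if it is kept. Give Wald 95% CIs (log scale for the RR), state the number of resamples and the seed, and report the share of resamples that did not converge. A sandwich SE that takes the score as known is not enough.

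The estimator may remain the score. Preferable, because the score model can itself fail to converge, is a logistic model with treatment and the covariates, averaging each infant's predicted risk under each dose to obtain the marginal RD and RR.

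Set the result beside SAP 7.1.1. If an unadjusted SE is also shown, note that it is too large if allocation was stratified on HIE and burden. In the strong stratified case it is 0.068 against a true SD of 0.0641, so a bootstrap SE near 0.059 would suggest a 13% gain (0.059/0.068) where the true gain is 8% (0.0588/0.0641).

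State the link, the Apgar time or times and the bilirubin measure. Reconcile the SAP 5.3 list with Protocol 9.4.2 on therapeutic hypothermia. SAP 7.1.1 needs no change on this account.

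The cost is one SAP paragraph and a short program, with no new data. The downside arises if the covariates carry no information: power with standardisation and bootstrap is 81.2/79.5% (unstratified/stratified), against 83.5/82.2% unadjusted and 82.1/80.3% for the score with its model SE, a loss of about 1-3 points.
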